Detection of bone erosions in PsA patients is usually achieved by conventional radiographs although the sensitivity is low (5). High-resolution peripheral quantitative CT (HR-pQCT) is a novel technique for detailed bone microstructure analysis with high reproducibility in assessing bony erosions (6). With its high spatial resolution of 130 µm, HR-pQCT exhibited a higher sensitivity in detecting erosion compared with radiograph and magnetic resonance imaging (MRI) (7). Recently, Finzel et al. described an indirect method to assess volume based on measurements of the width and depth of the erosions using HR-pQCT (8). Quantitative measurement of erosion volume can also be achieved (6). Using this method, erosion repair under biological disease-modifying antirheumatic drugs (DMARDs) treatment has been demonstrated in patients with rheumatoid arthritis (RA) (8, 9). Bone apposition at the margin of erosions (osteosclerosis) with the formation of a new cortical lining was associated with a decrease in erosion depth or width, which may indicate either periosteal or endosteal repair processes (8, 9). Valid measurement of erosion volume and the presence of osteosclerosis on HR-pQCT could be promising markers for erosion healing.

Detection of dactylitis is mainly by clinical assessment currently. With the advancement of ultrasound (US) imaging, it is lately discovered that the dactylitis was related with inflammation of pulley system from a pilot study (data not published). However, there are limited study on the change in inflammation of pulley system by US.

Interleukin 17 (IL-17) is a proinflammatory cytokine which produced by type 17 helper T cells (Th17). It is now considered to be a key cytokine in the pathogenesis of a number of autoimmune disorders in humans including PsA (10). IL-17 was also reported to be associated with the presence of joint erosion (11). Recently, secukinumab, an anti–interleukin-17A monoclonal antibody, was reported to be effective in reducing disease activity and decreased the rate of radiographic joint damage compared with placebo (12). However, whether healing of erosion could occur in PsA has never been evaluated. The US-detected longitudinal changes of dactylitis was not reported too.

On the other hand, osteophytes formation at the entheseal regions of the joints in PsA is distinctive feature compared with RA (13). The formation of osteophytes is tightly regulated by anabolic pathways, which resembles the pathogenesis of new bone formation in ankylosing spondylitis (AS). Tumor necrosis factor (TNF) inhibition was unable to halt the structural progression in AS patients (14-16), it also lacked efficacy in stopping the progression of osteophytes in PsA patients (17). Inhibition of IL-17 by secukinumab was effective in the treatment of both AS (18) and PsA (12). Secukinumab also decreased the rate of radiographic joint damage regarding to erosion and joint space narrowing (12). However, it is unknown if it has any effect in the progression of osteophytes. In an animal model, although over-expression of IL-17 alone failed to induce entheseal and periosteal bone formation, inhibition of IL-17 leaded to significant reduction of such bone formation in an IL-23 overexpression model (19). Moreover, IL-17A accelerates bone formation by stimulating the proliferation and osteoblastic differentiation of mesenchymal progenitor cells after injury (20). It is worth exploring if secukinumab could prevent the progression of osteophytes in PsA patients.

Aims and hypotheses to be tested:

Hypothesis

IL-17 inhibition by secukinumab could lead to healing of existing erosion, and prevent progression of osteophytes, and resolution of dactylitis in PsA patients.

Aims

The aim of this randomized, double-blind, placebo-controlled study is to evaluate the protective effects of secukinumab on the healing of joint erosion and prevention of progression of osteophytes in PsA patients using HR-pQCT and US.

Objectives

Primary outcome

Difference in changes in the volume of erosions on metacarpophalangeal joints (MCP) 2-4 measured by HR-pQCT at 24 and 48 weeks between secukinumab and placebo group.

Secondary outcomes

- The percentage of erosions with healing determined using HR-pQCT on MCP 2-4 at 24 and 48 weeks including 1). A decrease in erosion volume of ≥0.4 mm³ from baseline, and 2). The presence of grade 2 osteosclerosis at the margin of erosion.
- 2) Changes in volume and width of erosion using HR-pQCT at 24 and 48 weeks;
- 3) Changes in the height of osteophytes using HR-pQCT at 24 and 48 weeks;
- Marginal osteosclerosis (semi-quantitative and quantitative) using HR-pQCT at 24 and 48 weeks;
- 5) Changes in joint space volume using HR-pQCT at 24 and 48 weeks

Exploratory outcomes

- 1) Changes in US-parameters in dactylitis, enthesitis and synovitis at 24 and 48 weeks
- 2) Changes in van der Heijde-Sharp score on radiograph at 24 and 48 weeks.
- 3) Changes in patients-reported-outcomes (SF-36, Psoriatic Arthritis Impact of Disease (PsAID)) and functional disability (HAQ) at 24 and 48 weeks
- 4) Changes in biomarkers (Pro-C2, C-Col10, COMP, MCP-1, Dkk1 and sclerostin) at 24 and 48 weeks

Plan of Investigation:

Subjects 120 biologic DMARDs naïve PsA patients attending the outpatient clinic of the Prince of Wales Hospital (PWH), North District Hospital (NDH), Tai Po Hospital (TPH), Queen Elizabeth Hospital (QEH) and Tseung Kwan O Hospital (TKOH) who fulfilled the Classification Criteria for Psoriatic Arthritis (CASPAR), will be recruited. The main inclusion criteria are: 1) ≥18 years old; 2) without severe deformity in MCP joints (MCPJ) which would influence the longitudinal assessment of HR-pQCT; 3) with active disease, which is defined as three or more tender joints and three or more swollen joints, despite previous treatment with nonsteroidal anti-inflammatory drugs, disease-modifying antirheumatic drugs. These 120 patients will be screened for the presence of erosion at the head of MCPJ 2-4 using HRpQCT. The first 40 patients with erosion will be randomised in a 1:1 ratio to secukinumab (n=20) or placebo (n=20) group. Based on a study using high-resolution CT in 41 PsA patients, 41% of the patients had at least one erosion, and 90% of the erosions were in MCPs (5). The resolution of the highresolution CT is 0.4 mm, which is almost 5 folds lower than HR-pQCT (82 µm). Therefore, we estimated that over 1/3 of the PsA patients will have at least one erosion in MCPs. Thus, screening 120 patients using HR-pQCT should be adequate to recruit 40 patients with erosions on MCPJ 2-4.

All study procedures will be performed in PWH after recruitment from non-PWH site.

Randomisation will be performed using a computer-generated randomisation list provided by the hospital pharmacist, using a permuted blocks design with block sizes of 4 and 6. Allocation concealment will be ensured by the use of sequentially numbered, opaque, sealed envelopes. Treatment will be masked to patients and investigators.

Exclusion criteria are: 1) limited in ability to perform usual self-care, vocational, and avocational activities; 2) pregnancy; 3) previous therapy with biologic; 4) the presence of active inflammatory diseases other than PsA; 5) active infection in 2 weeks before randomization or a history of ongoing, chronic, or recurrent infections including tuberculosis; 6) history of hepatitis B & C; 7) history of malignant disease within the past 5 years (excluding basal cell carcinoma or actinic keratosis, in-situ cervical cancer, or non-invasive malignant colon polyps); 8) contraindications to secukinumab. The concomitant use of oral glucocorticoids (at a dose of \leq 10 mg per day of prednisone or its equivalent) and methotrexate (at a dose of \leq 25 mg per week) are permitted, provided that the dose will be stable.

The study will be approved by the Ethics Committee of the Chinese University of Hong Kong. Written informed consent will be obtained from all participants according to the Declaration of Helsinki and ICH-GCP guidelines.

Methods This is a 52-week, randomized, placebo-controlled, double-blind study. PsA patients will be randomised to either secukinumab or placebo group. All patients will be evaluated and treated according to the following protocol.

Study design

Treatment

The patients will be randomly assigned to the secukinumab group or placebo group. Patients will be followed-up at weeks 2, 4 and then every 12 weeks until week 52. Patients will receive subcutaneous placebo or secukinumab 150 mg once a week from baseline for 4 weeks, and then once every 4 weeks from week 4 onwards. The study flow is shown in Figure 1. Changes in the baseline treatment, e.g. the dosage of conventional synthetic DMARDs (csDMARDs) including methotrexate, leflunomide, hydroxychloroquine, or sulfasalazine or the addition of a new csDMARD (individually or in combination), as well as changes in the dosage or the addition of steroids or nonsteroidal antiinflammatory drugs were allowed after week 12 if the patient cannot achieve minimal disease activity (MDA) (Table 1) (see appendix 1 for the treatment protocol). For patients who fulfil the criteria for biologic DMARDs (bDMARDs) (Appendix 2) and are willing to be started on bDMARDs, the code will be broken, and they can either pay out of pocket or can apply for the Samaritan Fund for financial assistance, provided they must household-based pass а financial assessment (http://www.ha.org.hk/visitor/ha visitor index.asp?Content ID=10048&Lang=ENG&Dimension=100). Patients who have started bDMARDs apart from secukinumab will be excluded from the efficacy assessment. Adverse effects will be recorded.

Evaluation of disease activity and severity

At baseline and at each visit, we will quantify the extent of disease by evaluation of the multiple clinical domains of PsA. The following domains will be assessed: pain, physicians' and patients' global assessments, number of tender and swollen joints (using the 68 tender/66 swollen joint count), number of joints irreversibly damaged (baseline and week 52 visit only); enthesitis ((Maastricht Ankylosing Spondylitis Enthesitis Score (MASES), The Leeds Enthesitis Index (LEI) and the Spondyloarthritis Research Consortium of Canada Enthesitis Index (SPARCC Enthesitis Index).); number of digits with dactylitis; levels of acute phase reactant including erythrocyte sedimentation rate (ESR) and C-reactive protein (CRP) levels, Bath ankylosing spondylitis disease activity index (BASDAI), Bath Ankylosing Spondylitis Functional Index (BASFI) and the modified health assessment questionnaire (M-HAQ. For the skin domain, Psoriasis Area (BSA) and Psoriasis Activity and Severity Index (PASI) will be assessed in baseline and each visit. Quality of life will be assessed at baseline, week 24 and 48 which include HRQoL using the Short Form 36 (SF-36) Health Survey and the Psoriatic Arthritis Impact of Disease (PSAID) [21]. MDA will be used for assessment of treatment efficacy endpoint. A qualified dermatologist will be responsible for performing assessment of skin involvement (BSA, PASI) of the patients.

Composite disease activity will be assessed at baseline and at each visit according to the PASDAS (Table 2) (21). The PASDAS is calculated using the following variables: patient global VAS (0-100), physician global VAS (0-100), 66 swollen joint count, 68 tender joint count, CRP level (mg/ litre), Leeds enthesitis count (0-6), tender dactylitis count (0-20), and the physical component summary (PCS) scale of the Short Form 36 (SF-36) health survey. The PASDAS is then calculated by the formula [22]:

 $PASDAS = (0.18 \times \sqrt{physician global VAS})$

+ (0.159 × $\sqrt{\text{patient global VAS}}$)

 $- \ 0.253 \times \sqrt{SF\text{--}36} - PCS) + (0.101$

× LN [swollen joint count + 1])

 $+ 0.048 \times LN$ [tender joint count + 1])

+ $(0.23 \times LN \ [Leeds Enthesitis Count + 1])$

+ (0.377 × LN [dactylitis count + 1])

+ (0.102 × LN [CRP + 1] + 2 × 1.5, where LN is the natural logarithm.

The PASDAS was developed by GRAPPA based on real patient data from the GRAppa Composite Exercise (GRACE) project and it has been utilised by recent studies to monitor treatment response of biologic DMARDs including secukinumab and golimumab [23, 24].

At baseline, 24 and 48 weeks, Muscle-skeletal US will be examined for enthesitis, dactylitis and synovitis assessment; while X-rays of the hands, wrists, feet, hip and (X-ray pelvis for those with axial involvement) will be performed for the evaluation of erosion.

Laboratory assessments and inflammatory markers

Laboratory assessments at baseline, 24 and 48 weeks the end of study include fasting blood glucose, fasting lipid profile (total cholesterol, low-density lipoprotein-cholesterol [LDL-C], high-density

lipoprotein-cholesterol [HDL-C], triglycerides), fibrinogen, and uric acid. Total cholesterol is measured by an autoanalyzer enzymatic method. HDL-C is determined enzymatically with polyethylene glycol– modified enzymes. LDL-C is calculated by the Friedewald formula. If the triglyceride levels exceed 4.0mmoles/liter, the LDL levels are measured directly by ultracentrifugal single spin analysis. A total of 16 ml research blood will be collected for the following research use.

It has been suggested that chronic skin inflammation could lead to bone loss by IL-17-mediated inhibition of the WNT signalling pathway [25]. In order to investigate the effects of Secukinumab on the proposed pathway, the levels of WNT-inhibitors including Dickkopf-1 (Dkk1) and sclerostin will be measured with enzyme-linked immunosorbent assays (ELISA).

As joint space narrowing will be assessed (see below), relevant markers of cartilage formation, metabolism and turnover (Pro-C2, C-Col10, COMP and MCP-1) will be measured using ELISA according to the manufacturer's instructions [26, 27].

Safety Data Collection and Reporting

All possible side effect of the biologic and synthetic DMARDs used the study will be explained to the participants by the research nurse and the treating physician. To monitor the possible side effect, complete blood count, liver function tests and renal function tests will be performed every visit. Chest X-rays will be obtained at baseline and at the end of the study. The treating physician records all nonserious and serious adverse events, all reports of drug exposure during pregnancy, and all reports of misuse and abuse of the Novartis drug, other medication errors and uses outside of what is foreseen in the protocol, if necessary, make treatment adjustments in accordance with the protocol. Serious adverse events are defined as any adverse reaction resulting in any of the following outcomes: a lifethreatening condition or death, a significant or permanent disability, a medically significant event, hospitalization or prolongation of hospitalization, a congenital abnormality, or a birth defect. All adverse events from this trial will be reported to local IRB and Health Authority by the investigator according per requirement as holder of certificate of clinical trial. Any SAEs, reports of drug exposure during pregnancy and reports of Study Drug misuse or abuse, including initial and follow up reports, arising from the Study in subjects exposed to the Study Drug, as soon as it becomes available, but in any event within fifteen (15) calendar days of becoming aware of such information, will be forwarded to Novartis by transmitting it to Novartis Patient Safety team.

Erosion assessment by HR-pQCT

Image acquisition

Metacarpal bone erosion will be assessed at MCP 2-4 of the more severely affected or the dominant hand if both hands are equally affected using a HR-pQCT system (XtremeCT II; Scanco Medical AG, Bruttisellen, Switzerland). This system enables the simultaneous acquisition of CT slices with an isotropic resolution (voxel size) of 82 μ m. HR-pQCT scanning will be performed by a single investigator who is blinded to all the clinical information of the patients. A single examination will be performed for

measurements of MCP 2-4. An anteroposterior scout view will be used to define the region of interest (ROI). The scan region will be 80 slices distal and 242 slices proximal of the upper margin of the head of MCP3. Scan time will be around 8 min per patient and scan (8). The scans will be performed at baseline, 24 and 48 weeks.

Erosion identification and measurement of the width and depth

Erosions are defined as sharply marginated bone lesions with juxta-articular localisation with a cortical break seen in at least two adjacent slices, which are often accompanied by loss of the adjacent trabecular bone. Erosions will be differentiated from physiological breaks indicating entry of blood vessels by the linear shape and occurrence on predilection sites. Pseudo-erosions, structures similar to cortical breaks presented by osteophytes, will be excluded (22). Each of the erosions will be documented at baseline and 48 weeks. Assessment includes the palmar, ulnar, dorsal as well as the radial sides of MCP 2-4 heads investigating overall 322 2D HR-pQCT slices in the transversal, sagittal and coronal plane. Every erosion of each patient will be characterised by the maximal width and depth of the lesion in the axial, sagittal and coronal using the open source DICOM viewer Osirix V3.2 (Rosslyn, VA, USA).

Erosion volume

The volume of the erosions will be calculated according to the methodology published by Fouque-Aubert et al (6). The volume of erosions (using the entire volume of interest) will be determined by manually defining the ROI including the erosion (V1) or excluding it (V2). The volume of erosions will be then calculated as: Verosion= V1-V2; V =sum(A_i*0.082), where A1_i or A2_i is the area on slice i (mm²), including or excluding erosion, and 0.082 mm is the thickness of slice (Figure 2).

Osteosclerosis

The signs of bone apposition at the margin of the erosion will be documented (8, 9). Semi-quantitative scoring (0-2 scale) of osteosclerosis will be performed using coronal reconstructions as follows: grade 0 = 0%, grade 1 = 1.75%, grade 2 = 75.100% bone apposition along the surrounding bone (typical images were shown in Figure 3) (23). Quantitative osteosclerosis will also be calculated by choosing the area (width =15 vexols) around bone erosion in MCP2-4 as ROI (24). The density of the ROI will be calculated as the mean pixel attenuation of that area. 3D registration will be applied to obtain a consistent segmentation of the periosteal surface in the vicinity of the cortical break, which is highly important for accurate quantification of bone damage.

Defining the healing of erosion

This is the first study assessing erosion healing using HR-pQCT. Erosion healing is evidenced by a decrease in erosion volume and the presence of bone apposition at the margin of the erosion. Based on our preliminary data, the smallest detectable change of erosion volume, which was calculated on

the basis of 29 individual erosions as suggested by Bruynesteyn et al. (25), was 0.4 mm³. Meanwhile, a grade 2 osteosclerosis means dramatic bone apposition at the erosion margin (>75%). Therefore, a decrease in erosion volume of \geq 0.4 mm³ from baseline, and the presence of grade 2 osteosclerosis at the surface of erosion at 24 or 48 weeks is considered as strong evidence of erosion healing.

Osteophytes

The maximal height of each osteophyte will be documented by assessing the maximal distance between the surface of the osteophyte and the original cortical bone surface using the open source DICOM viewer Osirix V3.2 (Rosslyn, VA, USA) (17). The change of the maximal height between baseline and 52 weeks will be calculated.

Images will be evaluated by two independent readers blinded to the clinical data. Based on the posthoc analysis of a 6-months open-label randomized-controlled trial conducted by us (26), intra-observer reproducibility was 0.987, 0.994, 0.982, and 0.983 for erosion width, depth, volume and quantitative osteosclerosis, respectively. Inter-observer reproducibility as determined by intraclass correlation coefficient was: 0.977, 0.979, 0.962, and 0.974 for erosion width, depth, volume and quantitative osteosclerosis, respectively. Inter-reader agreement for the assessment of detecting the presence or the grade of osteosclerosis was also high (Kappa: 0.81~0.91).

Joint Space Width analysis

Volumetric joint space will be quantified using an algorithm developed by consensus from the Study grouP for eXtreme Computed Tomography in Rheumatoid Arthritis (SPECTRA) [33]. The 3-D JSW including mean (JSW.Mean, mm), maximum (JSW.Max, mm), minimum (JSW.Min, mm), SD (JSW.SD, mm), asymmetry [defined as JSW.Asymm = ratio of JSW.Max/JSW.Min,] as well as volume (JSV, mm³) will be calculated. Cuts through the sagittal and coronal planes (2-dimensional) will be automatically generated for visualization. A rheumatologist with HR-pQCT expertise will review all joints and score for degree of luxation (none, subluxation, luxation) and bone-on-bone contact (yes, no).

Ultrasound assessment of synovitis, dactylitis, enthesitis and digital pulleys

Each patient will undergo musculoskeletal ultrasound assessment of synovitis, dactylitis, enthesitis and the digital pulleys. The following anatomical sites and structures will be examined: (1) bilateral wrists, (2) bilateral metacarpophalangeal (MCP) joints 1-5, (3) bilateral proximal interphalangeal (PIP) joint 2-4, (4) interphalangeal joint of the thumbs, (4) bilateral distal interphalangeal (DIP) joints 2-4, (5) digits suspected of dactylitis, (6) digital pulleys A1, A2, A3, A4 and A5 of digits 2-4 of the more severely affected or the dominant hand if both hands are equally affected, (7) entheses including common extensor tendon at lateral epicondyle of humerus, the common flexor tendon at superior border of patella, patellar tendon at inferior border of patella and tibial tuberosity, Achilles tendon at calcaneus and plantar fascia at medial tubercle of calcaneus at baseline, week 24 and week 48 of follow-up. Baseline US will be performed on the same day, or within 1 week of clinical and laboratory assessment.

The US examination of each patient will be performed by 1 rheumatologist trained in musculoskeletal US and blinded to clinical and laboratory data. Each patient will undergo bilateral dynamic B-mode and power Doppler US examination.

OMERACT definitions for ultrasonographic pathologies, elementary lesions, definitions and scoring for enthesitis in spondyloarthritis and psoriatic arthritis are used (27-29) For the assessment of dactylitis, a variety of elementary lesions including flexor tendon tenosynovitis, joint synovitis, extratendinous soft tissue thickening, extensor tendonitis, enthesitis (finger extensor tendon, collateral ligaments, flexor fibrous sheaths, flexor pulleys, functional entheses), tenosynovitis, paratendonitis, synovitis, subcutaneous/peritendon tissue inflammation, proliferative and erosive bone changes will be assessed. Two measurements (transverse and longitudinal) will be done for assessing the thickness of the pulleys. The thickness of the A1, A3 and A5 pulley will be measured at the level of MCP, PIP and DIP level respectively. The A2 and A4 pulleys' thickness will be assessed in full extension, in correspondence to the proximal and middle phalanx, from their thickest sites. The US machine used is Esaote MyLab[™]Class-C equipped with a 6-18 MHz linear array transducer and 6-18 MHz hockey stick probe. The scanning technique will follow the European League Against Rheumatism (EULAR) standardized procedures for US imaging in rheumatology. The B-mode and power Doppler settings will be optimized and fixed for all the examinations.

Erosion and joint space narrowing assessment by radiographs

Radiographs at baseline, 24 and 48 weeks will be obtained and assessed by one radiologist and one rheumatologist who are masked to treatment groups. Radiological progression will be assessed using the Sharp-van der Heijde modified scoring method for PsA [34]. This method is based on the Sharp-van der Heijde method for assessing erosions and joint space narrowing of joints of hands and feet in RA. In addition to the joints evaluated for rheumatoid arthritis, the distal interphalangeal joints (DIPs) of the hands are assessed. It evaluates erosions in 20 joints in each hand and wrist, and six joints in each foot. These erosions are scored on a scale of 1–5 in the hands depending on the surface area affected and 0–10 in the feet. Total erosion scores range from 0 to 200 in the hands and 0 to 120 in the feet. Joint Space Narrowing (JSN) is assessed in 20 joints in each hand and wrist, and six joints in each foot on a scale of 1–4. The score of JSN ranges from 0 to 160 in the hands and from 0 to 48 in the feet.

Data processing and analysis Statistical analyses will be performed using the Statistics Package for Social Sciences (SPSS). Data will be analysed in an intention-to-treat manner. Patients who discontinued treatment or violated treatment protocol will be excluded from analysis. Missing data are assumed missing at random and will be treated using a multiple Imputation method (30). Based on the pilot study and our previous experience, the missing data is estimated to be less than 5%. Descriptive statistics will be used for demographic and clinical variables included frequencies, means and standard deviations, median and interquartile range. T-test, Mann-Whitney U test and Chi-square test will be used to evaluate differences in baseline characteristics between secukinumab group and placebo group. Changes of the outcome measurements between groups will be tested using t-test, Mann-Whitney U test, repeated measures analysis of variance (ANOVA) or Chi-square test where appropriate. Multivariate linear or logistic regression will be used to explore the association between the use of secukinumab and outcome measurements adjusting for baseline characteristics. A 2-tailed probability value of p < 0.05 is considered statistically significant.

Reference

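### The primary outcome is set at both 24 and 48 weeks with no decision rule, so its type I error is not fixed and a split result has no defined conclusion

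*Combined protocol and SAP*

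**What the plan says.** Under Objectives, the primary outcome is "Difference in changes in the volume of erosions on metacarpophalangeal joints (MCP) 2-4 measured by HR-pQCT at 24 and 48 weeks", secukinumab against placebo. Neither week is ranked above the other. The secondary outcomes carry the same two weeks, for example "The percentage of erosions with healing determined using HR-pQCT on MCP 2-4 at 24 and 48 weeks" and "Changes in volume and width of erosion using HR-pQCT at 24 and 48 weeks".

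Data processing and analysis gives one threshold for everything: "A 2-tailed probability value of p < 0.05 is considered statistically significant". It does not divide or order that 0.05. Outcome changes "between groups will be tested using t-test, Mann-Whitney U test, repeated measures analysis of variance (ANOVA) or Chi-square test where appropriate". No test is tied to the primary outcome, and no repeated-measures ANOVA term (group or group-by-time) is named as decisive. Baseline adjustment appears only in an exploratory role: "Multivariate linear or logistic regression will be used to explore the association between the use of secukinumab and outcome measurements adjusting for baseline characteristics". Baseline erosion volume is not named as a covariate.

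The Subjects paragraph randomises 40 patients, 20 per arm. Image acquisition schedules scans at baseline and both follow-up weeks.

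**The concern.** One primary outcome read at two time points needs a rule for turning two results into one conclusion. Without it, the same data can be reported as a success (one week crossed 0.05) or a failure (the other did not), and the false-positive rate depends on which reading is adopted later.

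Other sections do not settle the matter. The erosion identification section documents each erosion at baseline and week 48 only, while the healing definition accepts either follow-up week. With 20 patients per arm and no stated power, a result significant at one week only is a realistic outcome.

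**Working it through.** **Inputs from the plan.** Two time points, two-sided 0.05, 20 patients per arm. The only related figure that can be reproduced is the number randomised: 120 × 1/3 = 40 (the cited prevalences would give 120 × 0.41 × 0.90 = 44.3). That is a recruitment yield. The documents state no power, effect size, SD or overall error rate.

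**Assumptions.** One value per patient, all 20 per arm analysed, normal changes, and a correlation ρ between the 24- and 48-week changes, which the documents do not give. The two changes share a baseline. If the three scans have equal variance σ² and equal pairwise correlation r, each change has variance 2σ²(1 − r) and their covariance is σ²(1 − r), so ρ = 0.5. I therefore show ρ = 0.5, 0.7 and 0.9, with 0 and 1 as limits.

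**Either week counts.** P(either) = 0.05 + 0.05 − P(both).
- ρ = 0: P(both) = 0.05² = 0.0025, so P(either) = 0.0975 (= 1 − 0.95²).
- ρ = 0.5 / 0.7 / 0.9: bivariate normal P(both) = 0.0093 / 0.0165 / 0.0296, so P(either) = 0.0907 / 0.0835 / 0.0704.
- ρ = 1: the tests coincide, so P(either) = 0.05.

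**Simulation with t-tests** (no effect, 20 per arm, 200,000 runs, Monte Carlo error at most 0.07 points). Type I error, %:

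| Decision rule | ρ = 0.5 | ρ = 0.7 | ρ = 0.9 |
|---|---|---|---|
| Either week at 0.05 | 9.0 | 8.3 | 7.0 |
| Both weeks at 0.05 | 0.9 | 1.6 | 2.8 |
| One group test on the mean of the two changes | 5.0 | 5.0 | 4.9 |
| One named week only | 4.9 | 5.0 | 4.9 |
| 0.025 at each week | 4.6 | 4.3 | 3.6 |

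**Sensitivity of the either-week rate.** The analysed number may be smaller, because "Patients who discontinued treatment or violated treatment protocol will be excluded from analysis". At 15 per arm the rates are 9.1 / 8.4 / 7.0%. With skewed (log-normal) changes and 20 per arm they are 7.9 / 7.7 / 6.3%.

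**Split results.** P(split) = P(either) − P(both), now with a true and equal effect at both weeks (assumed).
- 80% power per week (standardised effect 0.909): 22.5 / 17.7 / 10.2%.
- 50% power per week (0.636): 33.9 / 25.6 / 14.7%.

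**Why the ANOVA term matters.** With equal effects and 80% power per week, the group term on the two changes has power 89.7 / 86.0 / 81.9%. The group-by-time term on those changes has 5%, because equal effects cancel in the difference.

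**Checks on the remedies.**
- *Fixed sequence.* With no effect at either week, any false claim requires the first test to reject, so the rate is 5%. If the first week has a real effect (80% power) and the second none, a false second claim occurs in 3.5 / 3.1 / 2.7% of trials.
- *Group-by-time with baseline as a level of time, uncorrected.* With equal SDs of change and change independent of baseline, the null rejection rate is 4.8 / 5.4 / 7.2% (60,000 runs). At ρ = 0.9 it does not hold 5%.
- *Baseline adjustment (ANCOVA against change score).* Variance falls by about 23 / 13 / 3% at assumed baseline–follow-up correlations of 0.5 / 0.7 / 0.9, and not at all at 0.95.

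**The case against.** The strongest reply is that the plan can be read without any inflation. If the word joining the two weeks means that both must succeed, the error is well under 5%. If repeated-measures ANOVA is the intended primary test and one term decides, it is about 5%. The test list most naturally means choosing by data type and distribution, not by p-value. This stands as far as it goes: inflation is not shown. But the plan states neither reading. The same two-week phrase is attached to nearly every secondary and exploratory outcome, where it looks like a measurement schedule rather than a success rule.

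A reader might infer more than the documents support:
- *That the error is about 10%, or ranges from 1% to 10%.* Such a range depends on the rules and correlations selected and is not a bound. Requiring both weeks gives 0.25% at ρ = 0. The upper end (9.7 to 9.8%) lets either ANOVA term decide, which no section says.
- *That it reaches 12% to 18%.* Those figures need either a test picked after seeing the p-values (12.5 to 14.0%) or erosions analysed as independent units (up to 17 to 18% with 3 per patient and an intraclass correlation of 0.5, both assumed). The plan states neither practice. It does measure at lesion level ("Every erosion of each patient will be characterised by the maximal width and depth of the lesion") and gives no per-patient value for the primary comparison, which is a reason to state one, not evidence of a wrong analysis.
- *That repeating erosion volume as a secondary outcome shows confusion about the primary week.* It may be a slip for depth, which is measured but absent from the outcome list. Little rests on it.
- *That the lack of baseline adjustment invalidates the comparison.* It costs precision, not validity.

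**Conclusion.** The concern holds as an unresolved decision rule. The plan names no primary week, no either-or-both rule, no sharing or order for the 0.05, no test for the primary outcome and no deciding ANOVA term.

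The either-week bounds of 5% and 9.75% need only a non-negative correlation and tests that each hold 5%. The values inside them rest on the assumed correlations, one value per patient and normal data, and are somewhat lower with skewed data. Under the stricter readings there is no inflation.

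A result significant at one week only would arise in about 10% to 34% of trials if effects are equal at both weeks, power is 50% to 80% per week and the correlation is 0.5 to 0.9. All three are assumptions, and the plan defines no conclusion for that case. The gap should be closed before unblinding, because a rule chosen afterwards would not be credible.

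**What to change.** Before the allocation is unblinded for analysis, amend the primary outcome under Objectives and the text of Data processing and analysis:

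1. Name one primary week; the choice is the sponsor's. Test it first at two-sided 0.05, and test the other week at 0.05 only if the first is significant.
2. Base both tests on one stated value per patient, for example total MCP 2-4 erosion volume.
3. Make the primary model an ANCOVA on the change at the named week, adjusted for baseline erosion volume. Keep the t-test and Mann-Whitney test as sensitivity analyses.

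Acceptable alternatives to step 1 are 0.025 at each week, or one named group test on the two changes. A group-by-time test with baseline as a level of time is acceptable only with a sphericity correction or as a multivariate test.

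**Cost.** Two sections change and no data are added, since the scans are already scheduled. The other week's claim becomes conditional, or each week faces a stricter level. Week 48, if chosen, is more exposed than week 24 to the treatment changes the Treatment section allows after week 12 and to its exclusion from efficacy of patients who start another biologic. The precision gain from baseline adjustment may be small if erosion volume is highly stable between scans.
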